9	SAI	FETY AND ADVERSE EVENTS	
	9.1	DEFINITIONS	
	9.2 9.3	RECORDING OF ADVERSE EVENTS	
	9.3 9.3.		
	9.3.		
	9.4	STOPPING RULES	
	9.5	MEDICAL MONITORING	42
10) D	OATA HANDLING AND RECORD KEEPING	43
	10.1	CONFIDENTIALITY	
	10.1	SOURCE DOCUMENTS	
			-

10.3 10.4	CASE REPORT FORMSRECORDS RETENTION	44 44
11	STUDY MONITORING, AUDITING, AND INSPECTING	45
11.1 11.2	STUDY MONITORING PLAN	45 45
12	ETHICAL CONSIDERATIONS	45
13	STUDY FINANCES	45
13.1 13.2	1 ONDER GOOD CONTROL OF THE CONTROL	45 45
14	PUBLICATION PLAN	46
15	REFERENCES	46
16	ATTACHMENTS	47
Pi	ruritus Visual Analogue Scale	50

List of Abbreviations

LIST OF ABBREVIATIONS

AE Adverse Event/Adverse Experience

BSA Body Surface Area

mCAILS Modified Clinical Assessment Scale of Severity for Index Lesion

Signs & Symptoms

CFR Code of Federal Regulations

CRF Case Report Form
CXCR3 Chemokine Receptor-3
CXCL9 Chemokines Ligands 9

DEGs Differentially Expressed Genes
DSMB Data and Safety Monitoring Board
FDA Food and Drug Administration

GCP Good Clinical Practice
GVHD Graft Versus Host Disease

HIPAA Health Insurance Portability and Accountability Act

IB Investigator's Brochure

IL-1 Interleukin-1

IND Investigational New Drug Application

IFNα Interferon Alpha IFNγ Interferon Gamma

IRB Institutional Review Board

JAK Janus Kinase LP Lichen Planus

LTR Lichenoid Tissue Reaction
MDC Myeloid Dendritic Cells
NRS Numerical Rating Scale
PDC Plasmacytoid Dendritic Cells
PGA Physician Global Assessment
PHI Protected Health Information

PI Principal Investigator

SAE Serious Adverse Event/Serious Adverse Experience

SOP Standard Operating Procedure

Study Summary

Title	Baricitinib (LY3009104) in the Treatment of Cutaneous Lichen Planus						
Running Title	Baricitinib (LY3009104) in LP						
Protocol Number	21-003075						
Phase	Phase II						
Methodology	Open-Label, Single Arm						
Overall Study Duration	21 to 24 weeks						
Subject Participation Duration	20 weeks						
Single or Multi-Site	Single Site						
Objectives	To evaluate the safety and efficacy of Baricitinib (LY3009104) in cutaneous LP as assessed by the change in Physician Global Assessment (PGA) of skin, oral mucosa, and hair, Body Surface Area (BSA), Index Treatment and Control Lesion by Modified Clinical Assessment Scale of Severity for Index Lesion Signs and Symptoms (mCAILS) score, Pruritus Visual Analog Scale (VAS), Verbal Rating Scale (VRS), Pruritus Numerical Rating Scale (NRS), and Skindex-16. To predict responses through the identification of unique biomarkers of LP at week 0 and utilizing RNA sequencing on responsive and non-responsive tissue at week 2.						
Number of Subjects	12						
Diagnosis and Main Inclusion Criteria	Non-pregnant adults with cutaneous LP						
Study Product, Dose, Route, Regimen	Baricitinib (LY3009104) 2 mg orally administrated, once daily.						
Duration of Administration	Drug will be administered from Day 0 through Week 16.						
Reference therapy	Baricitinib (LY3009104) is currently being used to treat subjects with rheumatoid arthritis and under investigation for atopic dermatitis and psoriasis.						
Statistical Methodology	The statistical analysis will provide descriptive summary statistics for categorical and continuous outcomes. Categorical variables will be described by their count and proportion of occurrence while continuous, normally distributed variables will be described by their mean and standard deviation; and continuous, non-normally distributed variables will be described by their median and range						

1 Introduction

This document is a protocol for a human research study. This study will be carried out in accordance with the applicable United States government regulations and Mayo Clinic research policies and procedures.

1.1 Background

Baricitinib (LY3009104) is an oral selective inhibitor of the Janus kinase (JAK)

family of protein tyrosine kinases with selectivity for JAK1 and JAK2, and less selectivity for JAK3 with potent activity on the cytokine IFN-γ. IFN-γ is a critical cytokine in the signaling of LP. This study is aimed at evaluating the effects of baricitinib (LY3009104) 2 mg once daily in subjects with cutaneous LP; however, other forms of LP including mucosal and scalp disease may also be present.

Lichenoid tissue reaction (LTR) includes lichen planus (LP), cutaneous lupus, dermatomyositis (DM), and graft versus host disease (GVHD). The pathogenesis of LP is incompletely understood; however, it is clearly T-cell mediated without a known auto-antigen. Lichen Planus (LP) is an inflammatory skin condition characterized by purple, polygonal, pruritic, papules and plaques. LP can affect any ectodermally derived tissues including: the skin (most commonly), nails, and mucous membranes. LP is thought to affect approximately 1-2% of the general population. Most cutaneous LP resolves within one to two years. Disease duration, in ascending order, is generalized cutaneous, non-generalized cutaneous, cutaneous and mucosal, mucosal, hypertrophic, and Lichen Planopilaris (hair LP). LP is the prototypical lichen tissue reaction (LTR). Modern theories of LP encompass three major stages: antigen recognition, lymphocyte activation, and keratinocyte apoptosis. A fourth stage, resolution, is a new and emerging topic. The occurrence of triggering factors in a genetically predisposed individual carrying LP-associated genes, results in disease development. During the initiation phase, damage to keratinocytes results in the release of DNA, RNA, and cathelicidin (LL37). These proteins can stimulate plasmacytoid dendritic cells (PDC) via toll like receptors 7, 9 (TLR7,9) which result in the release of interferon alpha (IFN α). IFN α can have both local and distant effects upon myeloid dendritic cells (MDC) as well as keratinocytes. Stimulated MDC interact with CD4+ T-helper cells and with the correct antigen. The antigen remains unknown but may represent a viral derived peptide. Signaling receptors on MDC will stimulate CD4+ T-helper cells via the release of Tumor necrosis factor alpha (TNFα), Interleukin-1 (IL-1), and -12. In addition, cluster of differentiation- (CD40) and CD40 ligand (CD40L) will result in the co-stimulation of the T-helper/MDC interaction. Stimulated CD4+ T-helper cells then release of interferon gamma (IFNy) and IL-2. These cytokines stimulate CD8+ T-cytotoxic cells. The stimulated CD8+ cells expressing Chemokine receptor-3 (CXCR3) will migrate to the dermal-epidermal junction following the release of chemokines ligands 9 (CXCL9), -10, -11. These chemokines are released by stressed and stimulated keratinocytes. The stimulated CD8+ cells will interact with the stressed keratinocytes and can induce apoptosis in with the proper and signaling receptors. This antigen also remains unknown but may be a self-antigen released by local stress. The major kill signals are TNFα, granzyme, and perforin. Fas and Fas ligand (FasL) are expressed on both keratinocytes and lymphocytes. Local CXCR3+ DC and Tregulatory cells may also modulate the local lichenoid response.

Based upon the critical role of CD8+ T-cytotoxic cells and IFN α and IFN γ signaling in LP, inhibition with Janus Kinase (JAK) 1, 2 inhibitors have significant therapeutic potential. Fitting with this, recent data has been published showing that IFN γ primed keratinocytes are vulnerable to CD8+ cytotoxic T-cells. This axis is dependent upon JAK inhibitors. Interestingly, this study also showed that the cytotoxic immune response was mediated by JAK2. The use of baricitinib in vitro was able to protect keratinocytes from cell mediated toxicity.

The current topical therapeutic options for LP are limited to topical corticosteroids, calcineurin inhibitors, and retinoids. Topical therapies are effective with limited disease but refractory disease is frequently encountered. Specific variants of LP, such as hypertrophic LP and localized cutaneous disease, are often refractory to all topical therapies and require systemic or skin-directed treatment with oral acitretin, methotrexate, glucocorticoids or light therapy. Long-term therapy with some of these oral medications is less desired due to adverse effects.

Therefore, additional oral and topical therapies would be highly desirable in hypertrophic and refractory localized cutaneous LP. As proof of principle, systemic JAK1, 2 inhibition with ruxolitinib was highly effective in steroid refractory graft versus host disease (GVHD).² Additionally, there was a recent case report of an exceptional responder to JAK1, 2 inhibition with ruxolitinib in refractory dermatomyositis (DM).³ As stated above, DM, GVHD, and LP share a similar histological pattern as well as signaling mechanism and, therefore, we would expect LP to respond similarly with systemic treatment. To test this concept, we would propose a single-center, exploratory, open-label, single-arm design study using systemic JAK1, 2 inhibitor for lesions of LP.

1.2 Investigational Agent

Baricitinib (LY3009104) is an inhibitor of the JAK family of protein tyrosine kinases. Mitogenic and inflammatory cytokines are strongly implicated in the pathogenesis of psoriasis, alopecia areata, atopic dermatitis, and lichenoid tissue reactions of the skin including LP. Baricitinib (LY3009104) inhibits the phosphorylation of STAT proteins and the production of pro-inflammatory factors induced by cytokines such as IL-23 and IFNγ, and has the potential to simultaneously reduce inflammation, cellular activation and proliferation of key immune cells (Investigator's Brochure). IFNγ is a key cytokine in the pathogenesis of LP.¹

Baricitinib (LY3009104) 2 mg orally administered, once daily in subjects cutaneous LP.

1.3 Preclinical Data

All preclinical data below is referenced from the IB. Please refer to the IB for more details.

Baricitinib represents a selective inhibitor of JAKs with excellent potency and selectivity for JAK2 (half-maximal inhibitory concentration [IC50] = 5.7 nM) and JAK1 (IC50 = 5.9 nM), and less potency for JAK3 (IC50 = >400 nM), or TYK2 (IC50 = 53 nM).

Although baricitinib potently inhibits JAKs, it does not significantly inhibit (<30% inhibition) a broad panel of 26 other kinases when tested at 200 nM (approximately 50 times the average IC50 JAK potency of baricitinib). Moreover, baricitinib demonstrates excellent potency in cell-based assays (IC50 values of 3 to 30 nM) relevant to the pathogenesis of autoimmune disease such as IL-2 stimulated phosphorylation of JAKs and STATs and IL-2 induced proliferation of T cells. This effect is not due to general cytotoxicity. Baricitinib also potently inhibited the phosphorylation of STAT proteins and the production of proinflammatory factors (IL-17 or monocyte chemotactic protein- [MCP-] 1, for example) induced by other important cytokines such as IL-23 and IL-6 with IC50 values in the range of 20 to 60 nM.

To estimate baricitinib potency in blocking JAK activity in hematopoietic cells in vivo where serum protein binding can be a significant factor, a whole blood assay was established that measures STAT3 phosphorylation in response to cytokine stimulation. Baricitinib blocked IL-6-induced STAT3 phosphorylation in human whole blood with an IC50 value of 104 ± 14 nM (n = 5). No effects on total STAT3 levels were observed at any concentration tested.

Baricitinib has been administered orally to CD-1 mice, Sprague Dawley rats, beagle dogs, and New Zealand white rabbits. In all toxicology species, exposures generally increased with increasing dose and were largely dose proportional to slightly greater than dose proportional. In general, exposures following repeated dosing were similar to single dose exposures, with some accumulation (approximately 2-fold) occurring in gravid rabbits. Gender differences were minimal.

Following administration of [14C]-baricitinib, minimal metabolism was observed in all species, as parent compound was the primary circulating entity in plasma and the bulk of radioactivity in urine and feces from all species was also attributed to parent compound. Furthermore, the toxicology species used to evaluate baricitinib are exposed to metabolites observed in humans. In mouse, rat, rabbit, dog, and human plasma, baricitinib had moderate protein binding with in vitro values ranging from approximately 45% to 56%.

Regarding multiple-dose toxicokinetics, the plasma toxicokinetics of baricitinib were evaluated in gravid Sprague Dawley rats and New Zealand white rabbits. Gravid rats were given daily oral doses of baricitinib beginning on Gestation Day (GD) 6 continuing through GD17. In a separate fertility and early embryonic development study, the plasma toxicokinetics of baricitinib were also evaluated in gravid Sprague Dawley rats administered daily oral doses of baricitinib for 2 weeks prior to cohabitation (Study Day 14) through GD6. In both studies, the exposures generally increased proportional to dose and no accumulation was observed. Gravid rabbits were administered daily oral doses of baricitinib beginning on GD7 and continuing through GD20. Exposures (Cmax and AUC) increased in a greater than dose-proportional manner and were

approximately 2-fold higher on GD20 compared to GD7, suggesting some accumulation of compound in rabbits.

Regarding drug distribution, quantitative whole-body autoradiographic techniques were used to determine the tissue distribution of drug-derived radioactivity in male and female pigmented (Long-Evans) and male non-pigmented (Sprague Dawley) rats following a single oral dose of [14C]-baricitinib. Distribution was extensive, with the highest concentrations of radioactivity being found in alimentary canal contents, bile, and urine. Distribution of drug-derived radioactivity was similar in pigmented and non-pigmented rats, with the exception of [14C]-baricitinib distributing to the uveal tract of the eye in pigmented rats, suggesting binding to melanin-containing tissues.

Elimination was nearly complete by 168 hours postdose in non-pigmented rats and 672 hours postdose in pigmented rats, except for low levels of radioactivity detectable in the dorsal caudal nerve, aorta, and uveal tract in pigmented rats. Specifically in the brain, radioactivity was below quantifiable limits (BQL) at all time points in pigmented rats, while in non-pigmented male rats low levels of radioactivity were detected in the brain (cerebrum: $0.189~\mu g$ equivalents/g of tissue; medulla: $0.231~\mu g$ equivalents/g of tissue) at 2 hours postdose, but were BQL at all other time points out to 168 hours. The low levels of radioactivity detected in the brain were likely from the vascular system and not directly in the brain tissue, thus penetration of baricitinib across the blood brain barrier is unlikely. The predominant routes of elimination were feces (in mice, rats with oral administration,) and urine (in rats with IV administration). Routes of elimination were similar in feces and urine in dogs.

The placental transfer and subsequent fetal exposure following a single oral dose of [14C]-baricitinib was evaluated in pregnant Sprague Dawley rats. [14C]-baricitinib-related radioactivity was widely distributed in fetal tissues at moderate levels through 8 hours postdose. Fetal tissues with the highest concentrations of drug-derived radioactivity were adrenal gland, gastrointestinal tract, myocardium, liver, and lung. Moderate to low levels of [14C]-baricitinib-related radioactivity were measurable in fetal brain and spinal cord through 8 hours postdose. All fetal tissue radioactivity concentrations were BQL by the final sampling time at 24 hours postdose. Lacteal excretion following a single oral administration of [14C]-baricitinib to lactating Sprague Dawley rats was also evaluated. Peak concentrations of [14C]-baricitinib-related radioactivity were observed at 4 hours postdose in milk and declined to low or BQL levels by 24 hours postdose. Exposure to radioactivity was approximately 39- and 18-fold greater in milk than in plasma based on area under the concentration versus time curve from zero to infinity (AUC0- ∞) and Cmax values, respectively. The elimination half-lives of radioactivity in plasma and milk were similar (2.61 and 2.72 hours, respectively).

Following a single oral dose of [14C]-baricitinib, the in vivo metabolism was evaluated in mice, rats, and dogs. Minimal metabolism was observed in all species, as parent compound was the primary circulating entity in plasma and the bulk of radioactivity in urine and feces from all species was also attributed to parent compound. In all species, the major metabolic pathway for these low level (<10% of dose) metabolites was oxidation. A low-level sulfate conjugate and glucuronide conjugate were also identified in mouse and rat feces and mouse and dog urine, respectively. Additionally, 2 to 3 low level unidentified metabolites were observed in various matrices in all species.

The toxicologic and toxicokinetic profiles of baricitinib were characterized in oral studies of up to 6 months in rats and 9 months in dogs. The safety of baricitinib was also characterized in juvenile rats. In the rat study, dose-limiting toxicity was identified at the high-dose level in both sexes. The high dose of 100 mg/kg/day was lowered to 60 mg/kg/day for females due to mortality occurring within the first 3 weeks of dosing that was subsequently determined to have resulted from gavage errors and not baricitinib toxicity. In males, mortality in high-dose (100 mg/kg/day) animals was mainly attributed to cardiomyopathy. This is a common background lesion in aging male rats, and it is possible that repeated dosing with baricitinib exacerbated this lesion. The 100-mg/kg/day dose was associated with plasma drug levels (unbound AUC0-24h 104.7 μ M*h) approximately 80-fold above those associated with a 4-mg once daily (QD) dose in subjects with

RA. Crystals, degeneration/regeneration, and/or tubular dilatation were observed in the kidney of males at 100 mg/kg/day and females at 100/60 mg/kg/day and considered adverse. Additional findings deemed adverse at ≥25 mg/kg/day included significant but reversible decreases in lymphocytes, generalized lymphoid depletion, and bone marrow hypocellularity, all presumed pharmacological effects of JAK inhibition. The no-observed-adverse-effect level (NOAEL) for QD administration of baricitinib for 26 weeks was 5 mg/kg/day (unbound AUC of 2.04 µM*h). Skeletal malformations (bent limbs and rib anomalies) and an increased incidence of skeletal development variations occurred in rat fetuses. Decreased pup weights were the dose-limiting effect in the rat pre-postnatal study. In juvenile rats, like adults, effects on body weight and the immune system were observed. Bone effects observed in the juvenile study included bacterial osteomyelitis with secondary fracture in one high dose animal, and exacerbation of femoral head and neck degeneration/atrophy.

In a 9-month dog study, administration of doses ≥ 3 mg/kg/day resulted in baricitinib-related early termination of dogs, suspension of dosing, adverse clinical effects, and anatomic and clinical pathology changes associated with clinical development of demodicosis and pyogranulomatous dermatitis; a secondary effect of the immunomodulatory pharmacology of baricitinib. Liver lesions consisting of minimal to moderate inflammatory cell infiltrates and/or inflammation and minimal to slight biliary hyperplasia, and associated increases in serum liver enzymes (aspartate aminotransferase [AST], alanine aminotransferase [ALT], alkaline phosphatase [ALP], gamma-glutamyltransferase [GGT]) were observed in dogs given ≥ 3 mg/kg/day. However, the relationship of the liver findings to baricitinib is uncertain because of the confounding severe demodectic mange and inflammation that were aggressively treated with Ivermectin and nonsteroidal anti-inflammatory drugs. Based on the adverse nature of the generalized demodicosis in animals given ≥ 3 mg/kg/day, the NOAEL is 0.5 mg/kg/day (unbound AUC of 0.74 μ M*h).

Overall, the major cell types affected by JAK inhibition in the nonclinical safety studies were lymphocytes and eosinophils. Decreases in lymphocytes and eosinophils in dogs were associated with clinical manifestations of immunosuppression including demodectic mange and bacterial, protozoal and/or yeast infections. Significant decreases in mean lymphocyte counts are generally not observed clinically. Given the general lack of correlation between nonclinical and clinical effects such as decreased lymphocyte counts with consequent infections, it seems useful to rely on the clinical safety database for consideration of safety margins, with the understanding that the consequences of immunosuppression may occur.

Regarding developmental toxicity, maternal and embryo-fetal toxicity occurred at the highest doses evaluated. At the high dose of 30 mg/kg in rabbits, maternal effects included mortality and decreased body weight gain, and decreased weight and rib/vertebral anomalies were observed in the fetuses. The NOAEL in rabbits for both maternal and fetal toxicity was 10 mg/kg/day. In the rat, maternal effects were decreased body weight gain and lacrimation at the high dose of 40 mg/kg; skeletal malformations (bent limbs and rib anomalies) and an increased incidence of skeletal development variations occurred in fetuses at the mid and high doses. The maternal NOAEL was 10 mg/kg, and the fetal NOAEL in rats was 2 mg/kg.

Regarding carcinogenicity, administration of baricitinib was well tolerated in both the 2-year rat and 6-month hRAS [001178-T (hemizygous), CByB6F1-Tg(HRAS)2Jic] transgenic mouse studies and did not produce neoplasms at any of the administered doses. Margins of safety based on unbound plasma exposure ranged from approximately 6-66-fold exposure at the maximum projected human dose. In rats, baricitinib administration was associated with increased survival and a decrease in proliferative changes, which included decreased incidences of neoplastic and hyperplastic lesions in the mammary gland and liver.

In a variety of in vitro binding and kinase assays, baricitinib did not demonstrate cross-reactivity for any of approximately 50 different receptors, channels, and transporters; or against approximately 30 non-JAK family kinases evaluated at 0.1 and 1 μ M, and 0.2 μ M, respectively. Safety pharmacology studies indicate that, at clinical doses, baricitinib is not expected to produce

effects related to central nervous system (CNS), cardiovascular (including human ether-à-go-go-related gene [hERG]), or respiratory function. At C_{max} exposures approximately 21-(dog) to 162-(rat) fold greater than the 4 mg clinical dose, the following findings were noted: altered autonomic activity, transient decreases in locomotor activity, and single occurrences of lacrimation at 100 mg/kg in a rat CNS evaluation; lower respiratory frequency and minute volume at 100 mg/kg in a rat respiratory evaluation; slight lowering of arterial pressure (2 to 3 hours postdose) and pulse pressure (7 to 18 hours postdose), and slight increase in heart rate (0 to 18 hours postdose) at 3 mg/kg in a dog cardiovascular evaluation; and no prolongation of the QTc interval in dogs. The IC50 for baricitinib on the hERG current was 161.5 μM. The exposure margin between expected human C_{max} plasma baricitinib (unbound) concentrations after a 4-mg dose (108 nM) and hERG IC50 inhibition is approximately 1400-fold, thus, indicating a low probability of a QT prolongation effect at therapeutically relevant doses.

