1.6 Risks and Benefits

Benefits:

Others with LP may benefit in the future from what we learn in this research study. It is possible their symptoms could also improve while being treated with this study drug

Risks:

The following adverse events were reported as common side effects associated with the use of Baricitinib (LY3009104):

• Very common (occurring in greater than or equal to 10% of subjects), common (occurring in 1-10% of subjects), and rare but serious (occurring in < 1% of subjects) side effects occurring in subjects. As of the clinical data cutoff date, approximately 548 healthy volunteers/Phase 1 study participants and 6555 patients have received baricitinib since the start of clinical trials. The most frequently reported TEAEs in healthy participants and participants with RA, Ps, AD, and SLE receiving 4-mg dose or lower are listed below.

Very Common (affecting more than 10 in every 100 patients)

No adverse event was seen in more than 10% of the rheumatoid arthritis, psoriasis, atopic dermatitis or systemic lupus erythematosus subjects treated with baricitinib (LY3009104).

Common (affecting less than 10 in every 100 patients)

Upper respiratory tract infection / nasopharyngitis (common cold)

Bronchitis / pharyngitis

Urinary tract infection (UTI)

Gastroenteritis (upset stomach)

Herpes zoster / herpes simplex activation (shingles / cold sore, respectively)

Influenza (flu)

Increase in blood chemistry labs (including lipids and CPK)

Headache

Atopic Dermatitis (treatable skin condition)

Thrombocytosis (increased blood platelets)

Nausea

Rare but Serious

Pulmonary embolism (blood clot in lung)

Deep vein thrombosis (blood clot typically in leg)

Cellulitis (severe skin infection)

Anemia

Hematologic and clinical chemistry lab abnormalities:

Baricitinib (LY3009104) taken systemically can inhibit the growth of blood cells. Low blood cells can make subjects more susceptible to infections by bacteria, virus, and fungi. The risk is low with systemic therapy and subjects will be monitored for any signs of inhibition of their blood counts.

Treatment with Baricitinib (LY3009104) has been associated with dose-related increases in CPK and total cholesterol, triglycerides, LDL-cholesterol (C), and HDL-C with stable LDL/HDL ratio. Observed increases have not led serious events or discontinuation of Baricitinib (LY3009104) in prior clinical trial participants. These lipid counts will be monitored throughout the study.

Infection risk:

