Temporary Interruption of Investigational Product: In some circumstances, patients may need to temporarily interrupt treatment as a result of AEs or abnormal laboratory values that may have an unclear relationship to investigational product. For the abnormal laboratory findings and clinical events (regardless of relatedness), specific guidance is provided for temporarily interrupting treatment and when treatment may be restarted. Retest frequency and timing of follow up laboratory tests to monitor the abnormal finding is at the discretion of the investigator. Investigational product that was temporarily interrupted because of an AE or abnormal laboratory value may be restarted at the discretion of the investigator.

- Absolute Neutrophil Count (ANC): Treatment should be interrupted if ANC < 1 x 109 cells/L and may be restarted once ANC return above this value
- Absolute Lymphocyte Count (ALC): Treatment should be interrupted if ALC $< 0.5 \times 109 \text{ cells/L}$ and may be restarted once ALC return above this value
- Hemoglobin (Hb): Treatment should be interrupted if Hb < 8 g/dL and may be restarted once Hb return above this value
- Hepatic transaminases: Treatment should be temporarily interrupted if drug-induced liver injury is suspected

Permanent Discontinuation from Investigational Product: Investigational product must be permanently discontinued if the patient or the patient's designee requests to discontinue investigational product. Discontinuation of the investigational product for abnormal liver tests should be considered by the investigator when a patient meets 1 of the following conditions:

- ALT or AST >8 x ULN
- ALT or AST >5 x ULN for more than 2 weeks after temporary interruption of investigational product
- ALT or AST >3 x ULN and total bilirubin level (TBL) >2 x ULN or international normalized ratio (INR) >1.5
- ALT or AST >3 x ULN with the appearance of fatigue, nausea, vomiting, right upper quadrant pain or tenderness, fever, rash, and/or eosinophilia (>5%)
- ALP >3 x ULN that is deemed to be of liver origin and drug-related
- ALP >2.5 x ULN and TBL >2 x ULN
- ALP >2.5 x ULN with the appearance of fatigue, nausea, vomiting, right upper-quadrant pain or tenderness, fever, rash, and/or eosinophilia (>5%)
- Investigational product should be permanently discontinued if any of the following laboratory abnormalities are observed:

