8.4 Stopping Rules

The stopping rules specified below are based on the knowledge available at study development. The stopping rule applies to the overall study. We note that the Adverse Event Stopping Rule may be adjusted in the event of either (1) the study re-opening to accrual or (2) at any time during the conduct of the trial and in consideration of newly acquired information regarding the adverse event profile of the treatment(s) under investigation. The study team may choose to suspend accrual because of unexpected adverse event profiles that have not crossed the specified rule below.

Accrual will be temporarily suspended to this study if at any time we observe events considered at least possibly related to study treatment (i.e. an adverse event with attribute specified as "possible", "probable", or "definite") that satisfy the following:

• If 2 or more patients in the first 6 treated patients (or 30% after the first 6 treated patients have been accrued) experience a grade 3 or higher non-hematologic adverse event.

We note that we will review grade 4 and 5 adverse events deemed "unrelated" or "unlikely to be related", to verify their attribution and to monitor the emergence of a previously unrecognized treatment-related adverse event.

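### The only numeric study-level rule (Section 8.4) leaves out hematologic events, so cytopenias that end a patient's treatment under Section 8.1 add nothing to the count that pauses accrual

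*Combined protocol and SAP*

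**What the plan says.** **Section 8.4, Stopping Rules.** The scope is explicit: "The stopping rule applies to the overall study". The trigger begins "Accrual will be temporarily suspended to this study if at any time we observe events considered at least possibly related to study treatment". The threshold is "If 2 or more patients in the first 6 treated patients (or 30% after the first 6 treated patients have been accrued"), and the patients counted are those who "experience a grade 3 or higher non-hematologic adverse event". The same section lets the study team suspend accrual for unexpected event profiles that have not crossed the threshold and lets the rule be adjusted during the trial. It also provides for review of grade 4 and 5 events judged unrelated or unlikely to be related.

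**Section 1.6, Risks and Benefits.** "Baricitinib (LY3009104) taken systemically can inhibit the growth of blood cells". The text then calls this risk low and promises monitoring of blood counts. Anemia is listed in the rare but serious group (below 1%).

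**Section 8.1, Definitions** (text on interruption and permanent discontinuation). Interruption limits are given for neutrophils, lymphocytes and hemoglobin. Then: "Investigational product should be permanently discontinued if any of the following laboratory abnormalities are observed". The list covers white cells, neutrophils, lymphocytes and hemoglobin.

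**Section 1.3, Preclinical Data.** "Overall, the major cell types affected by JAK inhibition in the nonclinical safety studies were lymphocytes and eosinophils". The rat findings at 25 mg/kg/day and above include "decreases in lymphocytes, generalized lymphoid depletion, and bone marrow hypocellularity, all presumed pharmacological effects of JAK inhibition". The section goes on to limit the clinical relevance of these findings.

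**Table-3.** A CBC is scheduled at screening and at every visit from Week 1.

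**The concern.** The plan treats severe cytopenia as serious enough to end treatment for one patient, but no number of such patients leads to a defined action for the study. The two layers of safety control are not connected for a risk that the protocol itself tells subjects about.

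At stake is whether new patients go on being enrolled while related severe cytopenias accumulate. Under the written rule nothing obliges anyone to pause and look. The documents give no reason for leaving hematologic events out.

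**Working it through.** **1. Is there a plan figure to reproduce?** No. Section 8.4 sets a threshold but gives no toxicity rate, error rate or operating characteristics for it.

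**2. The sections side by side**

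| Event, judged related | One patient (8.1) | Study-level count (8.4) |
|---|---|---|
| Hematologic value below an interruption limit | Interrupt | Adds 0 |
| Hematologic value below a permanent-discontinuation limit | Discontinue | Adds 0 |
| Grade 3 or higher non-hematologic event | Case by case | Adds 1 |

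The chance that hematologic events alone cross the rule is therefore 0 at any true rate, by definition.

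**3. What would counting them do?** Inputs: the limit of 2 in the first 6 (Section 8.4) and an assumed true per-patient rate *p* of related qualifying hematologic events. The documents give no such rate, so a range is shown. Patients are taken as independent.

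P(2 or more of 6) = 1 − (1 − p)^6 − 6p(1 − p)^5

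At p = 0.01: 1 − 0.94148 − 0.05706 = 0.00146, about 0.15%.
At p = 0.10: 1 − 0.53144 − 0.35429 = 0.11427, or 11.4%.

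For the 30% limb I checked after each patient up to 12 (Section 3.2), reading it as at least 30%. That means 3 events at patients 7 to 10 (0.30 × 10 = 3) and 4 at patients 11 and 12 (0.30 × 12 = 3.6, rounded up).

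| Assumed rate | 2 or more of first 6 | Ever crossed by patient 12 |
|---|---|---|
| 1% | 0.15% | not computed |
| 5% | 3.3% | 3.7% |
| 10% | 11.4% | 13.6% |
| 20% | 34.5% | 43.1% |
| 30% | 58.0% | 70.9% |

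The last column slightly overstates the practical effect, because a first crossing at patient 12 leaves no accrual to suspend. The table counts hematologic events only. Any qualifying non-hematologic events would come on top.

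**4. Do the other provisions act as a trigger?**

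- *Discretionary suspension (8.4).* It is permissive and worded for unexpected profiles, while reduced blood-cell growth is a listed risk.
- *Adjusting the rule (8.4).* This is a power to change the rule and sets off nothing by itself.
- *Grade 4 and 5 review (8.4).* It covers events judged unrelated or unlikely, so related cytopenias fall outside it.
- *Medical monitoring (8.5).* The principal investigator regularly assesses the number and type of serious events. No threshold is attached, and a laboratory cytopenia need not be serious.
- *FDA reporting (8.3.2).* A clinically important rise in the rate of serious suspected reactions must be reported. This is a reporting duty and does not suspend accrual.
- *Severe infection.* It would count as non-hematologic, but only after the harm had occurred.

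**The case against.** The strongest reply is that the protocol has already judged this risk and found it small. Section 1.6 calls it low, its list of common events contains no cytopenia, and Section 1.3 advises relying on clinical rather than animal data. Section 8.1 protects enrolled patients, while 8.4 only pauses accrual. These are different tasks, so there is no contradiction. Moreover, the UPIRTSO definition in 8.1 treats an event as unanticipated, and so unexpected, when it occurs more often or more severely than expected. A cluster of severe cytopenias, set against a risk called low, could then fall within the discretionary clause. At a 1% rate, counting the events would almost never change anything.

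Much of this stands, and it rules out three stronger readings that a reader might infer:

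- *That the protocol names lymphocytes and bone marrow as the drug's main toxicity targets.* It does not. The summary sentence in 1.3 names lymphocytes and eosinophils, in animals. Bone marrow hypocellularity is one of several rat findings at 25 mg/kg/day and above, against a no-adverse-effect level of 5 mg/kg/day.
- *That there is no study-level safeguard at all.* Discretionary suspension, safety monitoring and regulatory reporting all exist.
- *That 8.4 and 8.1 contradict each other, or that 8.4 decides whether the trial ends.* The rule only suspends accrual for a time, and the two sections differ in scope.

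What the reply does not supply is a trigger. Even on the generous reading of unexpected, a pause remains something the study team may choose. Statements about mean counts do not exclude severe individual cases, and 1.3 itself accepts that consequences of immunosuppression may occur. The setting also differs somewhat from the data behind the low-risk statement: Section 5.5 allows stable immunosuppressants for other conditions, and Section 1.5 provides for an extension at a higher dose. If the risk is indeed low, counting the events will rarely cause a pause.

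**Conclusion.** The point holds in limited form. The only pre-specified numeric study-level rule cannot respond to related hematologic events, including those for which the plan requires permanent discontinuation. The trigger probability from such events is 0 as written. Under the existing limit of 2 in the first 6 it would be between about 0.15% and 58.0% for assumed true rates of 1% to 30%.

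The zero follows from the text alone. The other figures rest on assumed rates, independence between patients, and every qualifying event being recorded as an adverse event and judged at least possibly related. They are not predictions of how often cytopenia will occur. The protocol's own description points to the lower end of the range. This is an inexpensive improvement to a safety rule, and it does not show that the rule as it stands is unsafe.

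**What to change.** Reconcile Section 8.4 with Sections 1.6 and 8.1. Amend the restriction to non-hematologic events in 8.4 so that related hematologic events which 8.1 already makes grounds for permanent discontinuation are visible to the study-level count. Which events and grades qualify is for the sponsor-investigator to set. The amended sentence should also say whether a laboratory value alone counts, because Supplemental 3 records it as an adverse event only if it causes signs or symptoms, is clinically significant or requires therapy.

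**Cost.** One phrase in 8.4, by amendment. No new tests are needed, because the CBC is already scheduled at each visit from Week 1. One limit remains: Week 1 and Week 3 visits held by video omit laboratory work (Section 6.3 and the Week 3 visit text), so those counts may be missing. The downside is a slightly higher chance of a temporary accrual pause: 3.3% in the first 6 patients at an assumed 5% rate and 11.4% at 10%, from hematologic events alone.
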